11.2.2.2 Treatment Durability

We will assess treatment durability descriptively as the number and percent of participants in each arm meeting the criteria specified in 9.3. We will report alongside these results the number and percent of participants eligible for the durability analyses (meaning that they achieved improvement of ≥8 points on KOOS Pain between baseline and 3 months, in the absence of surgical intervention or injection).

11.2.2.3 Longitudinal Outcomes

Longitudinal KOOS pain and ADL will be assessed with linear mixed-effects models including the baseline, 3 month, 6 month, and 12 month data¹⁵. These data will also be presented graphically by treatment group with means and 95% confidence intervals.

11.3 Interim Analysis

We have no planned interim analyses in this trail.

11.4 Subgroup analysis

We have no planned subgroup analyses in this trial.

11.5 Statistical analyses to handle missing data

We anticipate ~5% dropout at 3 months and ~10% at 12 months based on dropout rates from the Meniscal Tear in Osteoarthritis Research (MeTeOR) RCT⁹. We will address dropout and other forms of missing data first by reporting the number of subjects dropping out in each arm and the reasons for dropout. We will determine whether the frequency of these dropouts differs across study arms. We will examine the distribution of baseline covariates and baseline KOOS pain in subjects dropping out compared to those completing the study. Our primary assumptions

are that data will be missing at random (MAR), and that dropout will not depend on unobserved outcomes.

We will perform sensitivity analysis for missing data for our primary outcome of KOOS pain and our secondary outcomes of KOOS ADL, EQ-5D, strength measures, objective function measures, and treatment failure for our three primary hypotheses. We will use linear mixed effects models to analyze the continuous outcomes of KOOS pain, KOOS ADL, and EQ-5D. Models will be adjusted for timepoint, randomization arm, the randomization stratification factors of study site and baseline KL grade (0-2 vs. 3) as well as the baseline value of the outcome and enrollment date (prior to or after March 15, 2020). A timepoint by treatment arm interaction term will test whether change from baseline to 3 months differs between treatment arms. Linear mixed-effects models can handle imbalanced data and are appropriate for data that are missing at random.

For the categorical outcome of three month treatment failure we will use multiple imputation for missing data. To more accurately reflect the uncertainty in missing values, MI entails first creating multiple versions of the dataset, with missing values imputed under an assumed distribution, and then averaging results across these datasets. We will impute data using logistic regression by fully conditional specification, as recommended for dichotomous outcomes ^{16,17}. In the primary analysis, we will impute data under the missing at random assumption, assuming that missing data were associated with observed data (baseline KL grade, age, sex, BMI, baseline KOOS pain, baseline KOOS ADL, study site) ^{18,19}. Imputations will be done stratified by treatment arm. We will generate 20 imputed datasets and used the MIANALYZE procedure in SAS 9.4 to combine the results across the imputations. If the proportion of missing data for continuous outcomes exceeds 10%, an additional sensitivity analysis using multiple imputation will be conducted as outlined above.

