| 11.3 | Interim Analysis | 15 |
|--------|---|----|
| 11.4 | Subgroup analysis | 15 |
| 11.5 | Statistical analyses to handle missing data | 15 |
| 11.6 | Multiple testing | 16 |
| 12 Ana | alysis of Safety Endpoints | 16 |
| 12.1 | Adverse events | 16 |
| 12.2 | Serious adverse events | 17 |
| 12.3 | Analysis for AEs and SAEs | 17 |
| 13 Der | rived Variable Definitions, Coding, and QC Plan | 18 |
| 13.1 | Derived Variable Definitions and Coding | 18 |
| 13.2 | QC Plan | 19 |
| 13.3 | Code for Primary and Secondary Analyses | 19 |
| 14 She | ell Tables | 20 |
| 15 Bib | liography | 23 |
| | | |
| | | |
| | | |
| | | |

1 SAP Signatures

I give my approval for the attached SAP for the Treatment of Meniscal Problems in Osteoarthritis: The TeMPO Trial dated March 18, 2024

Statistician (Author)

Name:

[name]

Signature:

Date:

March 18 2024

Principal Investigator

Name:

[name]

Signature:

Date:

ranch 20, 2024

2 Trial Registration

The TeMPO Trial was first registered at clinicaltrials.gov with registration No. NCT03059004. on February 14, 2017.

3 Protocol

A manuscript detailing the TeMPO rationale and design features was published as follows1:

4 Summary of Changes to the Protocol or SAP

January 2024:

The COVID-19 pandemic began in the middle of TeMPO enrollment. We have updated the SAP to include a covariate in the multivariable models indicating enrollment date prior to or after the start of the pandemic (enrollment date (prior to or after March 15, 2020)) and to include a sensitivity analysis excluding participants enrolled between January and March 2020.

We added a secondary analytic approach of the primary outcome (KOOS Pain) of baseline-adjusted ANCOVA.

Rules for missing data in computing instruments (KOOS, EQ-5D) were clarified in section 13.4.

March 2024:

A sensitivity analysis excluding participants with protocol violations that affect study eligibility or data integrity was added (section 9.4).

5 Abbreviations and Definitions

| ADL | Activities of Daily Living |
|------|--|

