11.1 Primary Analysis

In the primary analysis we will test the 3 hypotheses outlined in section 7.1. As placebo is not used in practice, we do not consider tests involving Arm 3 as one of our multiple comparisons. For the primary analysis the alpha level is adjusted to 0.0167 to account for 3 comparisons. We will adjust for randomization arm, the randomization stratification factors of study site and baseline KL grade (0-2 vs. 3) as well as baseline KOOS pain and enrollment date (prior to or after March 15, 2020).

We will use linear regression as our main analytic approach, as our primary outcome of change in KOOS pain is continuous. The primary analysis will be complete case. Data will be summarized by treatment group with the number, mean, and standard deviation. 98.3% Cis will be used to summarize the three between-group comparisons of interest.

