11.2.2 Secondary Outcomes

All models will adjust for randomization arm, the randomization stratification factors of study side and baseline KL grade (0-2 vs. 3) as well as baseline value of the outcome and enrollment date (prior to or after March 15, 2020). We will adopt an intention-to-treat approach.

We analyze 3 month KOOS pain with an Analysis of Covariance adjusted for baseline KOOS pain. (This approach uses the 3 month value, adjusted for baseline, as the outcome, rather than the difference between three months and baseline).

11.2.2.1 Continuous secondary outcomes for baseline to 3 month change (KOOS ADL, EQ-5D, performance measures)

We will analyze continuous secondary outcomes with linear regression additionally adjusting for the baseline value of the outcome. In the case that some measures deviate from a normal distribution (e.g., number of repetitions in sit-to-stand test) we will consider data transformation or a generalized linear model (e.g., Poisson regression).

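### The 11.5 mixed model adjusts for baseline yet claims to test change from baseline, so the missing-data check cannot be compared with the primary analysis; the added ANCOVA repeats the primary model

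*SAP*

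**What the plan says.** **Primary model.** SAP 11.1 and the code in 13.3 fit a complete-case linear regression of the change in KOOS Pain on arm, site, KL grade and enrollment period, "as well as baseline KOOS pain and enrollment date (prior to or after March 15, 2020"). The primary estimate is therefore already baseline-adjusted.

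**Missing-data check.** SAP 11.5 uses linear mixed models for KOOS Pain, KOOS ADL and EQ-5D. The covariates are timepoint, arm, site and KL grade, "as well as the baseline value of the outcome and enrollment date (prior to or after March 15, 2020"). The next sentence names the test: "A timepoint by treatment arm interaction term will test whether change from baseline to 3 months differs between treatment arms". The visits used as responses and the covariance structure are not stated. Imputation of continuous outcomes is conditional: "If the proportion of missing data for continuous outcomes exceeds 10%, an additional sensitivity analysis using multiple imputation will be conducted".

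**Longitudinal model.** SAP 11.2.2.3 uses "linear mixed-effects models including the baseline, 3 month, 6 month, and 12 month data". It names no baseline covariate, but the opening line of 11.2.2 says that all models adjust for the stratification factors "as well as baseline value of the outcome and enrollment date".

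**Added ANCOVA.** SAP section 4 reports: "We added a secondary analytic approach of the primary outcome (KOOS Pain) of baseline-adjusted ANCOVA". Section 11.2.2 explains: "This approach uses the 3 month value, adjusted for baseline, as the outcome, rather than the difference between three months and baseline".

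**The concern.** A timepoint-by-arm interaction can measure change from baseline only if baseline is one of the response timepoints. Section 11.5 also has baseline on the right-hand side, so two adjacent sentences use it twice.

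A missing-data sensitivity analysis should agree with the primary analysis when nothing is missing; only then can a difference be put down to missing data. At the expected 5% or so dropout at 3 months, the 10% trigger for imputation is not met by dropout alone. This mixed model is then the only planned model-based check on missing data for KOOS Pain, KOOS ADL and EQ-5D. The analyses in 9.4 and 10.4 change the population or the visit window instead.

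The ANCOVA raises a smaller question: whether it adds any evidence to a primary model that already adjusts for baseline.

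**Working it through.** **Inputs.** From SAP 8.5: SD 16, target difference 5.3 points, alpha 0.0167, 194 per arm before dropout, 856 in total. From 11.5: about 5% dropout at 3 months. Assumed, because the SAP gives no value: correlation ρ between visits of 0.3, 0.5 or 0.7, equal for all pairs of visits, with SD 16 at follow-up too.

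**The plan's own figure.** Two-sided, 2 × (2.393 + 0.842)² / 0.33² = 192.2, so 193 against the stated 194: reproduced. Completers at 3 months: 856 × 0.95 / 4 = 203 per arm.

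**Reading A: baseline is a response and a covariate.** Write each visit's score as arm + time + arm×time + γ·baseline + other covariates + error. Subtracting the baseline row from the 3-month row removes γ·baseline, since it is the same in both. On complete data the interaction is therefore the raw difference in mean change.

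Let D0 and D1 be the arm differences at baseline and 3 months. Ignoring the other covariates, with n per arm:
- Interaction = D1 − D0, variance 4 × 16² × (1 − ρ) / n.
- Primary = D1 − ρ·D0, variance 2 × 16² × (1 − ρ²) / n.
- Variance ratio = 2 / (1 + ρ).
- Gap = −(1 − ρ)·D0, SD (1 − ρ) × 16 × √(2/203) = (1 − ρ) × 1.59.

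Power and CIs use the normal approximation (z = 2.393). Paired entries are 11.5 against primary.

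| | ρ = 0.3 | ρ = 0.5 | ρ = 0.7 |
|---|---|---|---|
| Variance ratio | 1.54 | 1.33 | 1.18 |
| SE increase | 24% | 15% | 8% |
| 98.3% CI half-width | 4.50 v 3.63 | 3.80 v 3.29 | 2.94 v 2.71 |
| Power for 5.3 points | 67% v 87% | 83% v 93% | 97% v 99% |
| SD of gap, nothing missing | 1.11 | 0.79 | 0.48 |
| Gap SD as share of 5.3 | 21% | 15% | 9% |

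One simulated complete data set (ρ = 0.5, 194 per arm, chance baseline imbalance −2.6 points) shows it: primary −6.14, 11.5 interaction −4.47, raw change difference −4.47.

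**With dropout.** Simulation: 1,500 runs per setting, 214 per arm, random intercept, 5% baseline-dependent dropout, two or four visits. The gap SD was 1.04–1.07 / 0.75–0.80 / 0.45 points with baseline used twice, against 0.02–0.06 with baseline used once (a response with a common mean across arms). A gap above 1 point occurred in 34–35% / 19–20% / 3% of runs, against none.

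**Reported SE.** Only with two visits and a random intercept bounded at zero is the SE also too small, by √((3 + ρ)/4) = 0.91 / 0.94 / 0.96. With four equally correlated visits and complete data it is right.

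**Reading B: follow-up visits only.** The covariate is proper, but the interaction now asks whether the arm effect varies over 3, 6 and 12 months. For a constant 5.3-point benefit (4,000 runs, alpha 0.0167) it rejected in 1.3–1.7% of runs, about the nominal level. The 3-month contrast from the same model rejected in 87–99%.

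**The ANCOVA.** If change = Xβ + δ·baseline + e, adding baseline to both sides gives 3-month value = Xβ + (δ + 1)·baseline + e. X, the cases and the residuals are the same, so every arm estimate, SE and p-value is the same. Only the baseline coefficient moves, by 1. In the simulations above, the arm coefficients differed by less than 3 × 10⁻¹⁴.

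**The case against.** Section 11.5 never says outright that baseline is a response; that is inferred from the interaction sentence. A sympathetic reader could carry over the primary model: change scores at follow-up visits as responses, baseline as a covariate, and the interaction included only to obtain the 3-month contrast. On that reading no precision is lost. This stands as a possible intention, but the sentence still names the interaction as the test, and under Reading B that test does not address the 3-month effect. The text needs correcting either way.

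Several limits also stand:
- Section 11.5 plans descriptive comparisons of dropout as well, so the mixed model is the only *model-based* check.
- The 10% trigger refers to missing data, not dropout alone, so imputation could still be reached.
- Section 11.2.2.3 conflicts only if the general adjustment line in 11.2.2 covers it.
- The sizes rest on assumed correlations, and the gap is small beside the 8–10 point clinically important difference cited in 8.5.
- The trial is not powered on a sensitivity analysis.
- The SAP does not claim that the ANCOVA is independent evidence.

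These points limit the consequence. They do not remove the contradiction.

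**Conclusion.** The concern holds. As written, the 11.5 check either tests an unadjusted change difference that departs from the primary estimate with no data missing (SD 0.48 to 1.11 points for ρ from 0.7 to 0.3), or names an interaction that does not test the 3-month effect. In the first case a reader cannot separate the effect of missing data from the loss of baseline adjustment.

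The damage is confined to the sensitivity analysis. On complete data the interaction is unbiased but less precise, and the primary analysis, sample size and alpha are untouched. The cancellation and the ANCOVA identity are algebra; the sizes depend on SD 16, 203 completers per arm and the assumed correlations. The ANCOVA duplication is harmless but adds no robustness. This should be fixed before the analysis is run.

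**What to change.** - **11.5:** use baseline once. Either keep it as a covariate with only follow-up visits as responses, or make it a response with a common mean across arms and no baseline covariate.
- **11.5:** name the visits and the covariance structure. Replace the interaction sentence with a statement that the estimate for hypotheses 1 to 3 is the model-based arm contrast at 3 months, with a 98.3% CI.
- **11.2.2.3:** say whether the general adjustment line applies. If baseline stays among the responses, exclude the baseline covariate explicitly.
- **11.2.2:** state that the ANCOVA gives the same arm contrasts as the primary model, or remove it.

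The cost is SAP wording and a few lines of code. No new data are needed, and the primary analysis does not change.

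### Section 11.5's fallback imputation for continuous outcomes names no continuous method, and its predictor list omits enrollment date and the own baseline of EQ-5D, strength and performance

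*SAP*

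**What the plan says.** SAP section 11.5 promises missing-data sensitivity analyses for KOOS pain and for the secondary outcomes, strength and objective function among them. It then gives the methods in two parts.

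- For three continuous outcomes: "We will use linear mixed effects models to analyze the continuous outcomes of KOOS pain, KOOS ADL, and EQ-5D". These models include the baseline of the outcome and enrollment date.
- For the binary outcome: "For the categorical outcome of three month treatment failure we will use multiple imputation for missing data". The method is stated thus: "We will impute data using logistic regression by fully conditional specification, as recommended for dichotomous outcomes". Missingness is assumed to relate to seven observed variables: "baseline KL grade, age, sex, BMI, baseline KOOS pain, baseline KOOS ADL, study site". Also: "Imputations will be done stratified by treatment arm", and "We will generate 20 imputed datasets".

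The imputation paragraph closes with the extension at issue: "If the proportion of missing data for continuous outcomes exceeds 10%, an additional sensitivity analysis using multiple imputation will be conducted as outlined above".

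Section 11.2.2 describes the models for the secondary outcomes. They adjust for arm, site and KL grade "as well as baseline value of the outcome and enrollment date (prior to or after March 15, 2020". Section 11.5 expects about 5% dropout at 3 months.

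**The concern.** The closing sentence points continuous outcomes to a recipe written for a yes/no outcome. It leaves three things open or ill-fitting: how a continuous score is imputed, whether the 3-month value or the change is imputed, and which predictors are used.

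The list contains the own baseline only for KOOS pain and KOOS ADL. For EQ-5D, the three strength measures, the walk, sit-to-stand and balance, it has no baseline of the outcome. Enrollment date is absent for every outcome.

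An imputation model that omits a covariate of the analysis model weakens the link between the imputed values and that covariate. The analysis then adjusts for a baseline that the imputed values largely ignore. At stake is a check that could be less reliable than the complete-case analysis it is meant to test. For strength and performance no other missing-data method is stated, because the mixed-model sentence does not name them.

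**Working it through.** **1. Variables in each model for a strength or performance outcome**

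| Variable | Analysis model (11.2.2) | Imputation list (11.5) |
|---|---|---|
| Arm | yes | yes (imputed by arm) |
| Site, KL grade | yes | yes |
| Own baseline | yes | no |
| Enrollment date | yes | no |
| Age, sex, BMI, baseline KOOS pain, baseline KOOS ADL | no | yes |

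**2. Size of the simulated trial**

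Section 8.5 gives 194 per arm for 0.33 SD, 80% power and type I error 0.0167. The normal formula gives n = 2(2.393 + 0.842)²/0.33² = 2 × 10.46/0.1089 ≈ 192.2, rounded up to 193. The t-based solution is 193.6, so 194 is reproduced. With dropout, 194 × 1.1 = 213.4, rounded up to 214. This figure is not in dispute and only sets the simulation size.

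**3. Precision**

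Set A simulated two arms of 214, a true difference of 0.33 SD, 20 imputations by arm, normal linear imputation, Rubin's rules and 300 replicates. The analysis adjusted for own baseline and enrollment period. Assumptions that are not in the SAP:

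- The baseline to 3-month correlation is 0.5 or 0.7.
- The listed predictors, represented by one variable, correlate 0.4 with the own baseline, so they carry 0.4² = 16% of its variance.
- The enrollment effect is 0.2 SD.

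Mean standard error of the arm difference with data missing completely at random (excess over complete case in brackets):

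| Correlation, missing | Complete case | Listed predictors, 3-month value imputed | Listed predictors, change imputed | Own baseline and enrollment date added |
|---|---|---|---|---|
| 0.5, 10% | 0.0878 | 0.0916 (4.3%) | 0.0921 (4.9%) | 0.0881 (0.3%) |
| 0.5, 20% | 0.0933 | 0.1005 (7.7%) | 0.1011 (8.4%) | 0.0939 (0.6%) |
| 0.7, 10% | 0.0721 | 0.0801 (11.1%) | 0.0742 (2.9%) | 0.0725 (0.6%) |
| 0.7, 20% | 0.0768 | 0.0920 (19.8%) | 0.0804 (4.7%) | 0.0773 (0.7%) |

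The listed predictors also gave the larger standard error whenever missingness depended on own baseline.

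Set B assumed correlations of 0.70 and 0.85, and 0.45 between the listed predictors and own baseline. It imputed the 3-month value and compared imputation without and with own baseline. At 0.85 the standard errors were 0.071 against 0.055 with 12% missing, and 0.082 against 0.059 with 20% missing. Before rounding, these excesses are 31% and 40%. A further run at about 12% missing gave 1–33%, depending on the correlation and on what was imputed. The overall range is therefore about 1–40%.

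Part of this excess is Rubin's variance overstating the true spread. In Set A at 0.7 and 20% missing, the empirical SD rose from 0.0762 to 0.0874 (14.7%) while the standard error rose 19.8%. The reported interval follows the standard error.

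**4. Bias**

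In Set A with data missing completely at random, or with missingness depending on own baseline equally in both arms, no bias was detectable. The largest deviation was 0.012 SD, in a run where the full data were themselves off by 0.006, with Monte Carlo error near 0.005.

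Bias appeared when missingness depended on own baseline in opposite directions by arm. At correlation 0.7 and 11% missing it was +0.112 SD if the 3-month value was imputed and −0.057 SD if the change was imputed. Complete case (−0.002) and imputation with own baseline and enrollment date (−0.003) were unaffected. This pair shows the reversal of sign under a deliberately strong pattern. It does not estimate the bias to expect.

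No run isolated the effect of omitting enrollment date alone.

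**The case against.** The strongest reply is that little hangs on this. The affected analysis is an additional sensitivity analysis, triggered only above 10% missing when about 5% dropout is expected at 3 months. EQ-5D also has a mixed model with own baseline and enrollment date, and KOOS pain, the primary outcome, has its baseline in the list. All of this stands and limits the weight of the point. Dropout, however, is not the same as a missing performance test, and the plan itself provides for the case above 10%.

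A reader might infer several stronger things that the document does not support:

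- *That sections 11.2.2 and 11.5 contradict each other on covariates.* They describe different models, one for analysis and one for imputation. Nothing removes own baseline or enrollment date from the analysis fitted after imputation. This is a mismatch between two models.
- *That the sponsor will impute continuous scores by logistic regression.* The SAP ties logistic imputation to dichotomous outcomes. The reference back may mean only the missing-at-random assumption, imputation by arm and 20 datasets. The continuous method is unspecified.
- *That omitting own baseline biases the result whenever missingness depends on it.* The simulations show bias only if that dependence differs by arm, and nothing in the SAP suggests that it will.

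It can also be said that the list does not exclude further variables. That is true, but it is the only list given, and an analyst following it would leave these variables out.

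**Conclusion.** The point holds as a defect in a conditional sensitivity analysis. The complete-case primary and secondary results are unaffected. Used with the listed predictors, the fallback is less precise than the complete-case analysis it checks. The excess in standard error is about 1–40% across the simulations, the upper end being measured against imputation with own baseline at an assumed correlation of 0.85. The range rests on assumed correlations of 0.5–0.85, 10–20% missing and an assumed weak link between the listed predictors and own baseline. It shows a span and is no forecast.

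Bias is possible only under missingness that relates to own baseline differently by arm, and no direction can be stated while the imputed quantity is unspecified. The point weighs most for strength and performance, which have no other stated missing-data method. For KOOS pain and KOOS ADL, only the unnamed method and the missing enrollment date remain.

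**What to change.** Replace the reference back in section 11.5 with a rule for continuous outcomes:

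- Impute the 3-month value separately by arm, using fully conditional specification with linear regression or predictive mean matching.
- Use the seven listed predictors plus the baseline of that same outcome and enrollment date in its two categories.
- Derive the change from the imputed value, fit the section 11.2.2 model and pool as already planned.
- State that this is the missing-data analysis for the strength and performance measures.

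Once own baseline is among the predictors of a linear imputation model, imputing the value or the change gives the same model, because the change is the value minus that baseline. The ambiguity over direction then disappears.

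In Set A the enlarged model kept bias to about 0.01 SD and brought the standard error to within about 3% of complete case in every scenario. The cost is SAP wording and a few more variables in the imputation step. Outcome baselines and enrollment date are already collected (section 10.2 and the shell tables), so no new data or participants are needed.
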